14.2. Sample Size Justification

The total sample size of 140 subjects who complete the study (Visit 3) was calculated to provide adequate power in detecting statistical superiority of the Test lens relative to prespecified thresholds for binocular distance, intermediate and near logMAR VA, CLUE vision Scores, Absolute toric rotation, rotational stability, rate of unacceptable lens fitting and rate of grade 3 or higher SLFs. All co-primary effectiveness and safety hypotheses are required to achieve statistical significance for the study objective to be satisfied, therefore no adjustment for multiple primary hypotheses is necessary. Each co-primary hypothesis will be tested using a 1-sided Type I error rate of 0.025.

Thresholds for hypotheses associated with CLUE vision, comfort and, handling scores are from a meta-analysis of 14 JJVCI clinical trials of toric and multifocal toric contact lenses used by habitual contact lens wearers aged 40 to 70 years¹². In this analysis, baseline CLUE scores (for subjects' habitual contact lenses) from 14 clinical studies were analyzed to establish thresholds reflecting the "real-world" performance of contact lenses wearers in this population

JJVC CONFIDENTIAL

with respect to CLUE vision, comfort, and handling scores. Thresholds for all other endpoints were based on clinically relevant margins.

Additionally, this study was also powered to test superiority for secondary endpoints with respect to CLUE vision, comfort and, handling scores and lens fit success using a 1-sided Type I error rate of 0.025. Secondary endpoints will be tested using a fixed sequence approach. Further details on the preservation of the study overall Type I error rate are in Section 14.4.

The sample size of 140 to complete yields at least 81% overall power to detect statistical superiority for all co-primary endpoints. This sample size provides a statistical power of at least 99% for each co-primary and secondary endpoint. To account for subject drop-out approximately 155 subjects will be enrolled to ensure at least 140 subjects complete the study.

Endpoint Domain	Endpoint	Statistical Test Type (Statistically Significantly)	Sample Size	Power (%)
Primary Efficacy	Distance (4m) Binocular Visual Acuity (logMAR)	Superiority: mean VA< 0.00	9	99.1
	Intermediate (64cm) Binocular Visual Acuity (logMAR)	Superiority: mean VA< 0.17	6	99.5
	Near (40cm) Binocular Visual Acuity (logMAR)	Superiority: mean VA< 0.17	29	99.1
	CLUE Vision Scores - Myopes	Superiority: mean score> 41	29	99.2
	CLUE Vision Scores - Hyperopes	Superiority: mean score> 36	23	99.0
	Absolute Toric Rotation $\leq 10^{\circ}$	Superiority: percentage>80%	140	>99
	Lens Stability with Blinks $\leq 5^{\circ}$	Superiority: percentage>80%	140	96.8
Primary Safety	Grade 3 or Higher SLFs (%)	Superiority: percentage< 5%	140	89.3
-	Unacceptable Lens Fitting (%)	Superiority: percentage<20%	140	>99
Secondary	CLUE Handling Scores: Hyperopes	Superiority: mean score> 46	15	99.2
Efficacy	CLUE Comfort Scores - Hyperopes	Superiority: mean score> 38	23	99.2
	CLUE Vision Scores - Hyperopes	Superiority: mean score> 41	42	99.1
	CLUE Handling Scores - Myopes	Superiority: mean score> 55	26	99.1
	CLUE Comfort Scores - Myopes	Superiority: mean score> 51	46	99.1
	CLUE Vision Scores - Myopes	Superiority: mean score> 46	55	99.0
	Lens Fit Success Rate (%)	Superiority: percentage>90%	140	99.8

 Table 6: Sample Size Estimates by Study Endpoint

This will be the first dispensing study since the lens design was changed hence, historical clinical data on the previous lens design has been used for the sample size calculations for any of the study endpoints except for toric rotation and lens stability with blinks. The changes made to the lens design improved the rotational performance of the contact lens and were not considered to impact the visual acuity or the subjective performance of the lens. Sample size estimates for toric rotation and lens stability with blinks were calculated using the results from

study while the sample size estimates for all other efficacy endpoints utilized data from study Historical data for each endpoint is summarized in Table 7 below.

		Value: Mean (SD) or
Endpoint Type	Endpoint	Percentage of Eyes
	Distance Binocular logMAR VA	-0.13 (0.078)
	Intermediate Binocular logMAR VA	-0.05 (0.092)
	Near Binocular logMAR VA	0.07 (0.120)
*Primary Efficacy Endpoints	Vision Scores – Hyperopes	54.32 (19.506)
	Vision Scores – Myopes	57.97 (20.282)
	Absolute Toric Rotation $\leq 10^{\circ}$	90.20%
	Lens Stability with Blinks $\leq 5^{\circ}$	100%
*Secondary Efficacy	Handling Scores - Hyperopes	67.52 (17.665)
Endpoints	Handling Scores - Myopes	71.48 (18.578)
	Comfort Scores - Hyperopes	57.95 (20.864)
	Comfort Scores - Myopes	64.97 (21.479)
	Lens Fit Success	100%
**Primary Safety Endpoints	Unacceptable Lens Fitting	0.0%
	Grade 3+ SLFs (Ocular Adverse Events)	0.0%

Table 7:	Historical	Data	bv	Endpoint
ruore /.	instorical	Data	υ,	Lindpoint

SD: Standard Deviation

*Summaries for primary efficacy and secondary endpoints were provided for the per-protocol population at the 1-week follow-up evaluation.

**Summaries for the primary safety endpoints were provided for the safety population; all available data was included

Co-Primary Efficacy Endpoint Sample Size Calculations:

Distance, Intermediate and, Near logMAR Visual Acuity

Sample size calculations for distance, intermediate and near visual acuity were carried out separately using one-sided, one-sample mean t-test, with a one-sided Type I error rate of 0.025 for each hypothesis using the *One-Sample T-Tests for Superiority by a Margin* procedure in Power Analysis & Sample Size (PASS2021) software Version 21.0.6 (NCSS LLC, Kaysville UT)¹³. To preserve the overall study power, each endpoint was powered to approximately 99%. The assumptions for averages and standard deviations were made based on historical values from previous studies (Table 7).

CLUE Vision Scores (Hyperopes and Myopes)

Sample size calculations for CLUE Vision scores were carried out separately for each sphere stratum (hyperopes and Myopes) using one-sided, one-sample mean t-test, with a one-sided Type I error rate of 0.025 for each hypothesis using the *One-Sample T-Tests for Superiority by a Margin* procedure in Power Analysis & Sample Size (PASS2021) software Version 21.0.6 (NCSS LLC, Kaysville UT)¹³. To preserve the overall study power, each endpoint was powered to approximately 99%. The assumptions for averages and standard deviations were made based on historical values from previous studies (Table 7).

Toric Rotation and Lens Stability

The reference rate for absolute toric lens rotation $\leq 10^{\circ}$ was based on the historical results of 90.2%. The reference rate for lens stability $\leq 5^{\circ}$ was based on the worst-case scenario of 99%, given the historical results show 100%. Toric lens orientation and rotational stability, respectively, are defined as a binary response:

Toric Lens Orientation : Y
=
$$\begin{cases} 1 & \text{if a subject eye has absolute toric lens rotation} \leq 10^{\circ}, \\ 0 & \text{Otherwise} \end{cases}$$

Rotational stability: $Z = \begin{cases} 1 & \text{if a subject eye has lens stability with blinks } \leq 5^\circ, \\ 0 & \text{Otherwise} \end{cases}$

Historical data of the Test lens indicates there is a high rate ($\geq 90\%$) for both toric lens rotation $\leq 10^{\circ}$ and rotational lens stability. Assuming a correlation of 0.70 between left and right eyes, a total of 5000 replicating trials were simulated with reference rate of 90.2% for the percentage of eyes with small ($\leq 10^{\circ}$) absolute toric lens rotation (or 99% of eyes with rotational stability). Given the high event rate of the binary outcome, Y=1, each replicated sample was analyzed using a Bayesian beta-binomial model with correlated binary data (Diniz et al; 2010)¹⁴. A non-informative prior distribution, beta (0.5, 0.5) was used to model P_T (proportion of eyes with absolute toric lens rotation $\leq 10^{\circ}$ [or lens stability $\leq 5^{\circ}$] for the Test lens). For each simulated trial, the 95% central posterior credible interval (CrI) constructed for the percentage of eyes with absolute toric lens rotation $\leq 10^{\circ}$ [or lens stability $\leq 5^{\circ}$] for the Test lens was calculated. The null and alternative hypothesis for determining statistical significance in both endpoints were $P_T \leq 80\%$ and $P_T > 80\%$, respectively. With the proposed sample size, each endpoint (percentage of eyes with absolute toric lens rotation $\leq 10^{\circ}$ and lens stability $\leq 5^{\circ}$) has at least 96% power, i.e., 96% of the estimated 95% CrIs had the lower bound above 80%.

Co-Primary Safety Endpoint Sample Size Calculations:

Grade 3 or Higher Slit Lamp Findings (SLF) and Unacceptable Lens Fitting

Grade 3 or Higher SLFs related to study lens wear was converted to a binary response as Y=1, if a subject eye has a clinically significant SLF, and Y=0 otherwise, for analysis purposes. Historical data show *none or an extremely low rate* (<1%) for clinically significant SLFs (Grade 3 or higher) for the test lens. Assuming a correlation of 0.70 between left and right eyes, a total of 5000 replicating trials were simulated with a reference rate of 1% (worse-case scenario). Given the rare event binary outcome of slit lamp findings, each replicated sample was analyzed using a Bayesian beta-binomial model with correlated binary data (Diniz et al; 2010)¹⁴. A non-informative prior distribution, beta (0.5, 0.5) was used to model P_T (proportion of eyes with Grade 3 or higher SLF for the Test lens). For each simulated trial, the 95% central posterior credible interval constructed for the percentage of eyes with grade 3 or higher SLFs for the Test lens was calculated. The null and alternative hypothesis for statistical significance

were $P_T \ge 5\%$ and $P_T < 5\%$, respectively. With the proposed sample size, at least 99% of the estimated 95% credible intervals had the upper bound below 5%.

As indicated in Table 6, co-primary safety endpoints were powered to at least $\sim 89\%$ individually, yielding a combined power of $\sim 88\%$. With respect to co-primary efficacy, each hypothesis, was powered to $\sim 99\%$, which provided a combined power of $\sim 92\%$. Therefore, the overall combined study power for co-primary safety and co-primary efficacy hypotheses is $\sim 81\%$.

Secondary Efficacy Endpoint Sample Size Calculations:

CLUE Vision, Comfort and, Handling (Hyperopes and Myopes)

Sample size calculations for the secondary endpoints of CLUE vision, comfort, and handling scores were carried out separately for each sphere stratum (hyperopes and Myopes) for all three CLUE domains using one-sided, one-sample mean t-test, with a one-sided Type I error rate of 0.025 for each hypothesis using the *One-Sample T-Tests for Superiority by a Margin* procedure in Power Analysis & Sample Size (PASS2021) software Version 21.0.6 (NCSS LLC, Kaysville UT)¹³. The assumptions for averages and standard deviations were made based on historical values from previous studies (Table 7).

Lens Fit Success

The reference rate for lens fit success was based on the worst-case scenario of 99%, given the historical results show 100% (Table 6). Lens fit is a binary response and is defined as follows:

Lens Fit Success :
$$Y = \begin{cases} 1 & \text{if a subjects' vision is optimized in 2 pairs or less} \\ 0 & \text{Otherwise} \end{cases}$$

Historical data of the Test lens indicates there is an extremely high rate (100%) for lens fit success. Assuming a correlation of 0.70 between left and right eyes, a total of 5000 replicating trials were simulated with reference rate of 99% for the percentage of eyes optimized in 4 lenses (2 pairs) or less. Given the high event rate of the binary outcome, Y=1, each replicated sample was analyzed using a Bayesian beta-binomial model with correlated binary data (Diniz et al; 2010)¹⁴. A non-informative prior distribution, beta(1, 1) was used to model P_T (proportion of eyes with optimized in 4 lenses or less). For each simulated trial, the 95% central posterior credible interval (CrI) constructed for the percentage of eyes optimized in 4 lenses or less was calculated. The null and alternative hypothesis for determining statistical significance were $P_T \leq 90\%$ and $P_T > 90\%$, respectively. With the proposed sample size, the percentage of eyes optimized in 4 lenses or less has at least 99% power, i.e., 99% of the estimated 95% CrIs had the lower bound above 90%.

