14.5. Primary Analysis

The co-primary efficacy analyses will be conducted on the ITT population, while co-primary safety analyses will be conducted on the safety population. All efficacy and safety analyses will be based on observed case data with no imputation of missing values.

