14.5.2. Co-Primary Safety Analyses

The primary safety analyses will be conducted on the safety population.

Grade 3 or Higher SLFs and Unacceptable Lens Fitting

Grade 3 of Higher SLFs (or Unacceptable lens fitting) will be analyzed using a Bayesian betabinomial model with correlated binary data¹⁴.

The Model:

Let Y (the percentage of eyes with grade 3 or higher SLFs [or unacceptable lens fitting]) be the sum of equicorrelated binary responses (Y_1 and Y_2 denotes left and right eyes, respectively) with probability of success p and correlation coefficient ρ .

The probability distribution of $Y = Y_1 + Y_2$ is obtained by the mixture of two variables. One of them follow a binomial distribution Bin(2, p) with probability of success p and mixing probability $(1 - \rho)$, and the other follows a modified Bernoulli distribution MBern(p), taking values 0 and 2, with probability of success p and mixing probability ρ :

$$P(Y = y | p, \rho) = (1 - \rho) Bin(2, p)I_{A1} + \rho MBern(p)I_{A2}$$

where $I_{A1} = \{0,1,2\}$, $I_{A2} = \{0,2\}$ and *p* is the probability of success (i.e. proportion of eyes with Grade 3 or Higher SLFs).

To overcome the complexity of the mixture likelihood, a latent variable Z_i , i = 1, 2 is introduced in the model to indicate in which component of the correlated binary model the observation y_i , i = 1, 2 belongs to, that is,

 $Z_i = \begin{cases} 1 & \text{if the observation belong to } MBern(p) \\ 0 & \text{if the observation belong to } Bin(2,p) \end{cases}$

The joint distribution of the augmented data (Y_i, Z_i) , i = 1, 2, is given by

$$\begin{split} P(Y = y_i, Z = z_i | \, p, \rho) \\ &= \rho^{z_i} \, p^{\frac{y_i z_i}{2}} \, (1-p)^{(2-y_i)\frac{z_i}{2}} \, (1-\rho)^{1-z_i} \, \begin{pmatrix} 2 \\ y_i \end{pmatrix} \, p^{y_i \, (1-z_i)} \, (1-p)^{(2-y_i)(1-z_i)} \end{split}$$

The probability p links to the regression variables through a logit transformation as follow: $logit(p) = \beta_o + \beta_1 lens$

It is assumed that β_o , β_1 and ρ to be independent with a non-informative prior N(0, 1000) for β_o and β_1 , and beta(0.5, 0.5) for ρ . The Metropolis sampler algorithm as implemented in the SAS/STAT MCMC procedure¹¹ will be used to estimate the posterior distributions of the parameters (β_o , β_1 , ρ). Inferences will be made based on a posterior credible interval for the relevant parameters.

Bayesian Estimation and Statistical Evaluation of Hypothesis:

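### Section 14.2 claims at least 99% power for every endpoint, but Grade 3+ slit lamp findings have about 89%, and the two rotation powers in Table 6 appear to be swapped

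*Combined protocol and SAP*

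**What the plan says.** All statements are in Section 14.2 of the combined protocol and SAP unless noted.

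- **General claim.** For 140 completers: "This sample size provides a statistical power of at least 99% for each co-primary and secondary endpoint". The sentence just before it gives at least 81% overall power for all co-primaries together.
- **Table 6, all at n = 140.** The row "Grade 3 or Higher SLFs" shows 89.3%. Absolute toric rotation within 10° shows >99%. Lens stability with blinks within 5° shows 96.8%. Unacceptable fit shows >99%.
- **SLF text.** For a true rate of 1% against the 5% threshold: "at least 99% of the estimated 95% credible intervals had the upper bound below 5" percent.
- **Combined-power paragraph, immediately after.** "As indicated in Table 6, co-primary safety endpoints were powered to at least" about 89% individually and about 88% combined. It then says each co-primary efficacy hypothesis was powered to about 99%, with about 92% combined for efficacy and about 81% overall.
- **Rotation inputs.** The sizing rate for absolute rotation is 90.2%, the historical result. The rate for stability "was based on the worst-case scenario of 99%, given the historical results show 100" percent. Both are tested against 80%, and the text claims at least 96% power for each.

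**The concern.** One simulation is reported as both 99% and 89%, and the general 99% sentence contradicts two cells of the table it introduces. The rotation rows are also in an implausible order. With the same n, eye correlation and prior, a true rate of 99% must be easier to show above 80% than a true rate of 90.2%, yet Table 6 gives stability the lower power.

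Sections 2.3 and 14.4 require every co-primary to succeed, and one failure also blocks all secondary tests. SLF is the weakest of the nine and is a safety endpoint. Anyone quoting the 99% sentence would understate the chance of missing it by roughly a factor of ten. A reader of Table 6 would also pick the wrong rotation endpoint as second weakest.

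**Working it through.** **1. The plan's own products.** The five visual acuity and CLUE vision rows of Table 6 multiply to 0.991 × 0.995 × 0.991 × 0.992 × 0.990 = 0.960. Taking each >99 entry as 0.99:

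- efficacy: 0.960 × 0.968 × 0.99 = 0.920 (stated about 92%)
- safety: 0.893 × 0.99 = 0.884 (stated about 88%)
- overall: 0.920 × 0.884 = 0.813 (stated about 81%)

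So the sponsor's overall figure depends on 89.3% for SLF. If all nine co-primaries sat at 99%, the product would be 0.99⁹ = 0.914. With 0.99 in place of 0.893 for SLF alone it would be 0.813 × 0.99 / 0.893 = 0.90.

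**2. The mean-based rows.** One-sample noncentral-t power at one-sided 0.025, using the Table 7 means and SDs, reproduces all 11 such rows of Table 6 within 0.1 point. At 140, 84 or 56 completers, as applicable, each is at least 99.88%. The 99% claim is true for these rows.

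**3. SLF, from the stated inputs.** The inputs are n = 140 subjects, p = 1%, eye correlation ρ = 0.70 and a beta(0.5, 0.5) prior on p. Success means that the upper 95% central credible bound is below 5%. I also put beta(0.5, 0.5) on ρ. That is an assumption for the sizing, because the plan gives this prior for ρ only in Section 14.5.

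From the mixture in Section 14.5.2, the probabilities for one subject are:

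- no eye: 0.3 × 0.99² + 0.7 × 0.99 = 0.98703
- one eye: 0.3 × 2 × 0.01 × 0.99 = 0.00594
- both eyes: 0.3 × 0.01² + 0.7 × 0.01 = 0.00703

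A grid posterior shows that success needs one of:

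- no bilateral case and at most 6 unilateral
- 1 bilateral and at most 4 unilateral
- 2 bilateral and at most 1 unilateral

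A Poisson hand check uses means 140 × 0.00703 = 0.984 (bilateral) and 140 × 0.00594 = 0.832 (unilateral). It gives 0.374 × 1.000 + 0.368 × 0.998 + 0.181 × 0.797 = 0.885. Exact enumeration gives **88.6%**, or 89.0% with ρ fixed at 0.70. Table 6 has 89.3%.

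**4. Rotation and stability, same method, lower bound above 80%.**

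| Endpoint | True rate | Recomputed | Table 6 |
|---|---|---|---|
| Absolute rotation ≤10° | 90.2% | 95.8-96.3% (96.8% with ρ fixed) | >99 |
| Stability ≤5° | 99% | 100% | 96.8 |

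The printed values match their inputs only when exchanged.

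**5. Sensitivity.** Section 14.5 says the "co-primary safety analyses will be conducted on the safety population", which covers everyone given a test article and so may approach 155 subjects. The planned analysis puts a normal prior on logit(p), not a beta prior on p.

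| SLF power | N = 140 | N = 155 |
|---|---|---|
| Sizing prior | 88.6% | 91.9% |
| Planned analysis prior | 93.9% (up to 96.5% with ρ fixed) | 95.6% |

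Absolute rotation is 96.6-97.5% under the analysis prior at N = 140, and 97.2-97.6% at N = 155 under the sizing prior.

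**6. Unacceptable fit.** No sizing rate is stated; Table 7 gives only the historical 0%. Power is 100% if the true rate is 1% or 5%, and about 96% if it is 10%.

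**The case against.** The strongest reply is that this is a reporting slip. The correct SLF figure is printed twice, in Table 6 and in the combined-power paragraph. It is carried into the 81%, which stands one sentence before the faulty claim, and the sample size does not depend on the 99% wording. That is right, and it limits the finding to a correction of the text.

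The 11% chance of missing SLF belongs to the sizing prior at N = 140. Under the planned analysis prior it is about 6% at N = 140 and about 4% at N = 155. A fair range is therefore about 4-11%. Even the lower end is well above the 1% that the text implies.

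The swap is inferred, because the simulation output is not in the documents. That stands too, so the output should be checked before the cells are changed. Nobody, however, has found a reading of the stated inputs that gives 96.8% for a 99% rate against 80%.

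**Conclusion.** The concern holds. The general 99% sentence and the SLF 99% sentence are wrong as written. SLF power is about 89% under the stated sizing assumptions (1% rate, ρ = 0.70, beta prior, N = 140) and stays below 99% in every variant tried. The two rotation entries in Table 6 appear to be exchanged: the inputs support about 96-97% for absolute rotation and over 99% for stability. The statement that each co-primary efficacy hypothesis was powered to about 99% is loose for the same reason.

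At least 81% overall is not an error. It is conservative because five of its nine factors use the minimum n (6 to 29) instead of the planned completers. At 140/84/56 completers, assuming independent endpoints and power near 1 for the rest, overall power is 0.968 × 0.893 = 0.86 on the sponsor's figures, or 0.958 × 0.886 = 0.85 recomputed. Exchanging the rotation cells leaves the product unchanged.

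**What to change.** Corrections to Section 14.2:

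1. Replace the general sentence with: about 89% for Grade 3 or higher SLF, about 96-97% for absolute toric rotation, and about 99% or more for each other co-primary and secondary endpoint. State the reference rate assumed for unacceptable fit, since its >99% depends on it.
2. In the SLF paragraph, replace the 99% with the simulated value (89.3% in Table 6).
3. Check the simulation output for the two rotation endpoints. If it confirms the swap, exchange the Table 6 cells: absolute rotation 96.8, stability >99.
4. In the combined-power paragraph, except absolute rotation from the statement that each efficacy hypothesis has about 99%.

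Optional clarifications: say that 81% is a lower bound built on minimum sample sizes, with about 85-86% at the planned completers under independence. Note that the safety and Visit 1 rotation analyses may include more than 140 subjects, and that SLF power is about 94% under the planned analysis prior at N = 140.

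The cost is a few sentences and two table cells. Enrolment, tests, thresholds and decision rules stay as they are; the stated SLF power becomes less favourable. Section 14.1 says the stand-alone SAP will be finalised before database lock, so the corrected figures can be carried there as well.

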was a single-arm, single-masked dispensing evaluation of multifocal toric investigational lenses with 4 study visits (fitting visit, optimization visit, then follow-up visits after 1 and 2 further weeks of wear). The subjects were required to have distance spherical component of their refraction in the range of either -1.25 D to -3.75 D, or +1.25 D to +3.75 D; and refractive cylinder in the range of -1.00 D to -1.50 D with axes in the range of $90^{\circ}\pm 30^{\circ}$. Ninety-five subjects were enrolled, of whom 9 were screen failures that were not administered the test article. Of the 86 subjects (48 myopes and 38 hyperopes) who wore the study lens, 2 discontinued the study and 1 was excluded from cohort. As a result, the Per Protocol population was 83 subjects (48 myopes and 35 hyperopes). There were no adverse events reported for the study.

was a bilateral, single-masked, single-visit, non-dispensing crossover study of investigational multifocal toric lenses with cylinder corrections of -1.00 and -1.75 diopters. Lens performance in terms of rotation, initial comfort and lens handling was assessed for participants representing four segments of the population (myopic with with-the-rule astigmatism, myopic with against-the-rule astigmatism, hyperopic with with-the-rule astigmatism, and hyperopic with against-the-rule astigmatism). A total of 102 subjects were enrolled, and all completed the study. No adverse events were reported.

In addition to these multifocal toric studies, a series of studies have been performed on the non-toric multifocal version of the study lens during the development of Acuvue[®] Oasys 1-Day Max Multifocal. Further details of the safety profile of these related lens types are included in the CR-6542 Investigator's Brochure⁴.

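### The 81% overall power holds only at an assumed 1% slit-lamp rate; the protocol's history does not make 1% a worst case or 81% a floor

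*Combined protocol and SAP*

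**What the plan says.** Section 14.2 gives the slit-lamp power as the share of 5000 trials "simulated with a reference rate of 1% (worse-case scenario") in which the 95% credible interval lay below 5%. The setting is "Assuming a correlation of 0.70 between left and right eyes". Table 6 reports 89.3% for this test with 140 subjects.

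The overall claim, earlier in the same section, is: "The sample size of 140 to complete yields at least 81% overall power to detect statistical superiority for all co-primary endpoints". The closing summary of the safety calculations gives about 81%, without the floor. All co-primary hypotheses must succeed (sections 2.3 and 14.4), and "Each co-primary hypothesis will be tested using a 1-sided Type I error rate of 0.025".

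The evidence for the 1% is a historical rate of 0.0% in Table 7, described in the text as none or below 1%. Table 7 gives neither the study nor the number of eyes. Section 1.5 describes the prior studies. The third one is the closest in design: "Of the 86 subjects (48 myopes and 38 hyperopes) who wore the study lens", and it had no adverse events.

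**The concern.** Zero events in a modest sample do not show that the rate is at most 1%. If higher rates are compatible with the history, 1% is a planning assumption, and power computed at 1% is a conditional figure.

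The label matters here because the slit-lamp test has the lowest power in Table 6 and its power falls quickly between 1% and 3%, while the requirement is 5%. A lens with a true rate of 2% would meet the requirement but could easily fail the test. A sponsor who reads the 81% as a minimum would not see that risk.

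**Working it through.** **Inputs.** From section 14.2: 140 completers, 155 enrolled, correlation ρ = 0.70, a beta(0.5, 0.5) prior on the rate in the sizing simulation, and the Table 6 powers. From section 14.5.2: success if the upper limit of the 95% central credible interval is below 5%, and an N(0, 1000) prior on the logit coefficients in the planned analysis. From section 1.5: 86 wearers in the third study, 40 enrolled in the first, and 35 enrolled less 3 screen failures = 32 in the second (assumed exposed). The single-visit non-dispensing study had 102.

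**Model (section 14.5.2).** For eye-level rate p:
- P(no eye affected) = (1 − ρ)(1 − p)² + ρ(1 − p)
- P(one eye) = (1 − ρ)·2p(1 − p)
- P(both eyes) = (1 − ρ)p² + ρp

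Power is the exact multinomial sum over all outcomes for which the posterior probability of p < 5% is at least 0.975.

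**Step 1: reproduce the plan at 1%.** With the sizing prior, ρ estimated and n = 140, slit-lamp power is 88.6%. With ρ fixed at 0.70 it is 89.0%. Table 6 has 89.3%, so it reproduces. Taking entries given as above 99 as 0.99 and treating endpoints as independent:
- efficacy: 0.991 × 0.995 × 0.991 × 0.992 × 0.990 × 0.99 × 0.968 = 0.920
- safety: 0.893 × 0.99 = 0.884
- overall: 0.920 × 0.884 = 0.813

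These match the plan's 92%, 88% and 81%. One sentence in section 14.2 says at least 99% of the slit-lamp intervals succeed. That does not reproduce and conflicts with Table 6.

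**Step 2: what zero events exclude.** The one-sided 95% upper limit solves P(no eye affected)ⁿ = 0.05.

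| History assumed | Limit, subjects | Limit, eyes at ρ = 0.70 |
|---|---|---|
| 0 of 86 (third study) | 1 − 0.05^(1/86) = 3.4% | 2.65% |
| 0 of 158 (40 + 32 + 86, all dispensing) | 1.9% | 1.45% |
| 0 of 260 (adding the 102) | 1.1% | 0.88% |

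Check of the first row: 0.3 × 0.9735² + 0.7 × 0.9735 = 0.9658, and 1 − 0.9658 = 3.4%. Treating the 172 eyes as independent still gives 1.7%.

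At a true 1%, P(no eye affected) = 0.3 × 0.9801 + 0.7 × 0.99 = 0.9870, and 0.9870⁸⁶ ≈ 0.33. At 2% the chance of 0 of 86 is about 0.10.

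**Step 3: power at those rates.** The other eight tests multiply to 0.910. Each cell is slit-lamp power / overall power.

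| True eye rate | Sizing prior, n = 140 | Planned prior, n = 140 | Planned prior, n = 155 |
|---|---|---|---|
| 1.0% | 88.6% / 81% | 94% / 86% | 96% / 87% |
| 1.45% | 74% / 68% | 83% / 76% | 86% / 78% |
| 2.0% | 54% / 49% | 65% / 59% | 68% / 62% |
| 2.65% | 34% / 31% | 43% / 39% | 46% / 42% |

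The sizing prior at n = 155 gives 84%, 72%, 53% and 32% overall.

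**The case against.** Several objections have force.

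- **The arithmetic is right.** At 1% the plan's figures reproduce, and the rate is printed with the calculation. This stands: the fault lies in the label and the floor.
- **The denominator is inferred.** Table 7 names no study, and its footnote says all available safety-population data were used. Section 1.5 also points to an Investigator's Brochure that was not available here. So 0 of 86 cannot be asserted as the basis, and the limits are conditional on the history assumed. Counting the 102-subject study gives 0.88%, which would support the label. But that study involved one visit and no dispensed wear, so it says little about findings over two weeks.
- **1% is conservative against the centre of the history.** Averaging over the posterior from 0 of 86 under the sizing prior gives about 86% overall power; 0 of 158 gives about 89%. A flat prior with 0 of 86 gives about 78%. So 81% is a reasonable planning figure, but an average is not a minimum.
- **The low figures use unfavourable settings.** The test is run on everyone who wore a lens, which may exceed 140, and with a different prior. The ranges above include both.

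Two stronger readings are not supported. A reader might infer that the plan rules out a failure risk above about 11% for the slit-lamp test; the documents nowhere say so. A reader might also infer that the trial is underpowered or has only 31–68% power. Rates at or below 1% fit zero events best, and at 2.65% a result of 0 of 86 would occur only 5% of the time.

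The similar label for lens fit ("The reference rate for lens fit success was based on the worst-case scenario of 99"%) concerns the last secondary hypothesis in a gated sequence. It does not enter the 81% and is minor.

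**Conclusion.** The concern holds in a limited form. The figure of about 81% is correct if the true Grade 3 or higher rate is 1% of eyes, with 140 subjects, ρ = 0.70, the sizing prior and independent endpoints. It is not a lower bound, and the history shown does not establish 1% as the worst case. At 1.45% to 2.65%, the limits from the dispensing histories, overall power is below 81% under every prior and sample size tried: 68–78% at the lower rate and 31–42% at the upper. The direction is robust; the size depends on the denominator behind Table 7, the prior, and how many subjects enter the safety population. The 32 exposed in the second study is an assumption.

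**What to change.** In section 14.2, slit-lamp paragraph, describe 1% as the assumed rate. Restate the overall claim as about 81% power if the true Grade 3 or higher rate is 1% of eyes. Add one line with slit-lamp and overall power at 1.5%, 2% and 2.6%, computed with the prior planned for the analysis. State the study and number of eyes behind the 0.0% in Table 7, and reconcile the sentence claiming at least 99% with the 89.3% in Table 6. Relabelling the 99% for lens fit success in the same way is optional.

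The cost is a few words and a re-run of the existing simulation at three rates. The stated power becomes conditional and looks less favourable. Sample size, thresholds and decision rules stay as they are.
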